### **Benefits to Subjects**

Participants may or may not benefit from participating in this feasibility pilot trial. Benefits that could occur are better glycemic control because of the lifestyle intervention for participants randomized to the M4M condition. Results from this research will help refine the delivery of this intervention with the intent of increasing the efficacy of the intervention.

### **Privacy of Subjects**

This study is slightly above minimal risk. Participants will be provided a copy of the consent form that will describe the study and what is being asked of them if they decided to participate, how the information they share will be used, the risk and benefits of participating, their rights regarding opting out, and their private information will not be shared with anyone outside of the research project. In addition, the study team contact information of the Principal Investigator and the UConn Health Human Protection office will be provided to each participant.

During transcription of post-intervention interview audio recordings, participants' names will be replaced with their study ID number to permit linking of statements with de-identified survey data. Uniquely identifying statements (e.g., names of family members, locations) will be deidentified during transcription (e.g., replace husband's name with "[HUSBAND]"). After the transcripts have been checked for accuracy, the audio recordings will be deleted. Interview transcripts will be stored on a password-protected research drive accessible only to appropriate research staff. Study

team members not involved in the conduct or analysis of the interviews will not have access to the audio recordings or private identifiable information about participants.

Data from uninterested or ineligible potential participants: Contact information will be stored in a password protected file (REDCap project) with an indication that they are not eligible and reason(s) for ineligibility.

### **Confidentiality of Data**

The study team will protect the confidentiality of the information participants provide. However, confidentiality cannot be guaranteed.

The following security protocols will also be applied to all data: physical protections - all data will be stored on secure servers behind firewalls (e.g., REDCap hosted by UCHC, password-protected UConn/UCHC drives such as OneDrive or InCHIP research drive). All hard copy files will be locked in secure cabinets; logical protections – data will be password protected and/or encrypted; and access protections – access will be granted to data on a need-to-know basis only. All records consisting of personal identifiers will be destroyed upon completion of the study by shredding of the hard paper copy, redacting the PHI/PII from the hard paper copy, and/or destruction of the electronic files. Only relevant study staff will have access to participant PHI/PII. Analytic datasets will not include PHI/PII. Interview recordings will be deleted after transcription.

### **Budget/Resources**

Funding for the Meals 4 Moms study has been provided by the Clinical Research and Innovation Seed Program (CRISP).

### **Dissemination**

We plan on disseminating study results via publication of scientific articles, presentation at scientific conferences, and/or dissemination to the public (e.g., social media posts, infographics for a general audience).

COVER PAGE

Official Title: Feasibility Trial of a Lifestyle Intervention for Pregnant People with Gestational Diabetes

NCT Number: NCT06227247

Document Date: 2/12/2026

Statistical Analysis Plan

We will conduct data management and descriptive analyses using SAS 9.4 (SAS Institute, Inc., Cary, NC). We summarized participant characteristics and feasibility and acceptability outcomes, overall and by treatment condition. We will report recruitment and retention using a CONSORT diagram specific to feasibility pilot trials. We will export transcripts auto-generated by Webex to Excel. One member of the research team will listen to the recording and correct the transcript, and a second team member will listen to the recording to confirm the corrections. We will conduct a rapid qualitative analysis of participant feedback to inform continued development of the Meals4Moms program.

Feasibility Outcomes

Below we detail our feasibility outcomes, how they will be measured, benchmarks for assessing feasibility, and how we will use resulting information to inform the design of the efficacy trial. This table is also included in the study protocol (document dated 1/31/24).

Feasibility outcome	How measured	Benchmark	How information will inform design of efficacy trial
Recruitment	Recruitment rates will be calculated from the number of patients approached and reasons for ineligibility and non-participation.	At least 75% of the patients screened as eligible should be recruited but the trial will not be feasible if recruitment uptake is 50% or less; we anticipate recruiting 4-5 participants per month	We will compare yield from different recruitment approaches and finalize our approach for the efficacy trial based on the most effective and efficient approaches. We will examine whether any eligibility criteria are excluding an inordinate proportion of otherwise eligible women, and if so, reassess scientific and practical necessity of each eligibility criterion. If recruitment rates are lower than expected, we will adjust recruitment timelines or modify our recruitment strategy or consider a second clinical site.
Retention	Proportion of participants who complete any aspect of the follow-up assessment	$\geq 80\%$ retention in each arm with 65% or less retention indicating that the main trial is not feasible	If retention is lower than expected, we will explore reasons for drop-out and modify the protocol to address these challenges.
Receipt of intervention	Records of # meals ordered per week; Records of # of	$\geq 80\%$ ordered meals based on 21 meals per week	If compliance with meal ordering does not meet our targets, we will explore alternative strategies for increasing compliance with the interventions and modify the protocol to address these

	exercise sessions		challenges. We will also describe engagement with other aspects of the intervention website using back-end data from the intervention website and qualitative feedback from post-intervention interviews with participants randomized to the M4M condition.
Intervention acceptability	Participants in both conditions will be asked if they would participate again if they had GDM in the future and if they would recommend the program to a friend with GDM (5-item Likert scales of likelihood)	$\geq 80\%$ of participants indicate “likely” or “very likely” on both measures of acceptability	We will interview participants in the M4M condition who have completed the trial (after delivery) to understand feasibility and acceptability issues and use their feedback to modify study procedures or intervention materials before moving to a full-scale efficacy trial. We will also examine responses to additional questions assessing frequency of use of and ratings of helpfulness and relevance of other aspects of the M4M intervention.

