### **Feasibility Outcomes**

Below we detail our feasibility outcomes, how they will be measured, benchmarks for assessing feasibility, and how we will use resulting information to inform the design of the efficacy trial.

Feasibility outcome	How measured	Benchmark	How information will inform design of efficacy trial
Recruitment	Recruitment rates will be calculated from the number of patients approached and reasons for ineligibility and	At least 75% of the patients screened as eligible should be recruited but the trial will not be feasible if recruitment uptake is 50% or less; we anticipate	We will compare yield from different recruitment approaches and finalize our approach for the efficacy trial based on the most effective and efficient approaches. We will examine whether any eligibility criteria are excluding an inordinate proportion of otherwise eligible women, and if so, reassess

	non-participation.	recruiting 4-5 participants per month	scientific and practical necessity of each eligibility criterion. If recruitment rates are lower than expected, we will adjust recruitment timelines or modify our recruitment strategy or consider a second clinical site.
Retention	Proportion of participants who complete any aspect of the follow-up assessment	≥80% retention in each arm with 65% or less retention indicating that the main trial is not feasible	If retention is lower than expected, we will explore reasons for drop-out and modify the protocol to address these challenges.
Receipt of intervention	Records of # meals ordered per week and # of produce bags ordered per week; Records of # of exercise sessions	≥80% food budget spent based on \$266 per week ≥80% completed sessions with exercise trainer based on number of sessions eligible to complete	If compliance with meal ordering and completion of exercise sessions does not meet our targets, we will explore alternative strategies for increasing compliance with the interventions and modify the protocol to address these challenges. We will also describe engagement with other aspects of the intervention website using back-end data from the intervention website and qualitative feedback from post-intervention interviews with participants randomized to the M4M condition.

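### The SAP and the protocol set different benchmarks for receipt of intervention, so whether receipt is met can depend on which document is used

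*SAP*

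**What the plan says.** Both documents contain a table of four feasibility outcomes. The SAP introduces its table with "This table is also included in the study protocol (document dated 1/31/24"). The benchmarks for recruitment, retention and acceptability agree. Those for receipt of intervention do not.

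- **Protocol, Feasibility Outcomes.** The food measure is "Records of # meals ordered per week and # of produce bags ordered per week", and exercise sessions are also recorded. There are two benchmarks. The first is at least 80% "food budget spent based on" $266 per week. The second is at least 80% "completed sessions with exercise trainer based on number of sessions eligible to complete". The response is conditioned on both components: "If compliance with meal ordering and completion of exercise sessions does not meet our targets".
- **SAP, Feasibility Outcomes.** The measure is "Records of # meals ordered per week; Records of # of" exercise sessions, and produce bags are not mentioned. The single benchmark is at least 80% "ordered meals based on 21 meals per week". The response is conditioned on food alone: "If compliance with meal ordering does not meet our targets".

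Elsewhere the protocol describes the food component only as a credit budget. The Meals 4 Moms section gives $266 per week, which participants divide between meals and produce as they choose. Subject Compensation gives a maximum of $2926 over 11 weeks. A quota of 21 meals per week appears nowhere in the protocol supplied.

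**The concern.** The SAP presents its table as the protocol's, but an analyst following one document could report receipt as met while an analyst following the other reports it as missed. The measure, the benchmark and the response all differ in the same direction, so a broken table in the PDF does not explain the difference.

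Two things are at stake. The first is which refinement follows: under the SAP row, poor attendance at trainer sessions triggers nothing. The second is that two definitions in force at once leave room to report the more favourable one. The SAP benchmark also fits the delivered intervention poorly, because a participant who uses all her credits but buys a good deal of produce counts as under-receiving.

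**Working it through.** **Inputs from the documents.** Weekly budget $266 (protocol, Meals 4 Moms). Up to 11 weeks and $2926 in total (protocol, Subject Compensation). Receipt thresholds of 80% (both tables). 21 meals per week (SAP only).

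**The plan's own figure.** $266 × 11 = $2926, which reproduces exactly. The budget figures are internally consistent.

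**The two food thresholds.**
- Protocol: 0.80 × $266 = $212.80 per week, or 0.80 × $2926 = $2340.80 over 11 weeks.
- SAP: 0.80 × 21 = 16.8 meals per week, or 0.80 × 231 = 184.8 meals over 11 weeks (21 × 11 = 231).
- The rules coincide only if meals average $266 / 21 = $12.67 and nothing is spent on produce.

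**Route 1: trainer sessions (no price assumption).** Take an arm with at least 80% of 21 meals ordered, at least 80% of budget spent and under 80% of eligible sessions completed. It meets the only SAP benchmark and misses one of the protocol's two.

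**Route 2: meal price (assumed, no produce bought).** The documents give no prices, so a range is shown.

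| Average price | Calculation | SAP | Protocol food rule |
|---|---|---|---|
| $10 | 17 meals = 17/21 = 81%; cost $170, and 170/266 = 63.9% | met | missed |
| $12 | 17 meals = 81%; cost $204, and 204/266 = 76.7% | met | missed |
| $14 | $212.80 / 14 = 15.2 meals, and 15.2/21 = 72.4% | missed | met |
| above $15.83 | $266 / 16.8 = $15.83, so the full budget buys fewer than 16.8 meals | cannot be met from credits alone | can be met |

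**Route 3: produce (assumed $12.67 per meal).** 16.8 meals cost 16.8 × $12.67 = $212.80 (using the unrounded price), which leaves $266 − $212.80 = $53.20. Full spend with more than $53.20 per week on produce therefore meets the protocol food rule at 100% and misses the SAP. At 90% of budget spent with 20% of that on produce, meals ordered are 0.90 × 0.80 = 72% of 21: protocol met, SAP missed.

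**The session denominator.** The protocol plans an initial trainer meeting and then biweekly reviews, over 8 to 11 weeks on average. Depending on delivery date and on whether the initial meeting counts, that is roughly 4 to 6 sessions. For one person, 80% then means 4 of 4 (0.80 × 4 = 3.2), 4 of 5 (4.0) or 5 of 6 (4.8). What counts as an eligible session is not defined, and at these numbers the definition matters.

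**The case against.** The strongest counter-argument is version control. The SAP cites a protocol dated 1/31/24, and the date of the protocol supplied is not visible. The SAP may simply carry the table from another version. That would explain the mismatch without removing it, because the SAP states the row as its benchmark.

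Several stronger readings are tempting but unsupported:

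- **That receipt is a go/no-go criterion, or that the SAP could pass the trial with no trainer sessions attended.** Only recruitment (50% or less) and retention (65% or less) carry a not-feasible cutoff. A missed receipt target leads to exploring other strategies and modifying the protocol.
- **That the protocol requires both benchmarks.** It lists two and does not say how they combine. Zero attendance misses one of them; whether receipt as a whole is then missed is not stated.
- **That individual participants pass or fail.** Neither document says whether 80% is an arm mean, a pooled total or a share of participants.
- **That the benchmark was chosen after the data were seen.** The SAP is dated 2/12/2026 and one sentence is in the past tense, but the surrounding text is in the future tense and nothing shows when the benchmark was set. Selective reporting is a risk here, not a finding.

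It is also fair to say that the SAP still records exercise sessions, so only their threshold is missing, and that every food example depends on assumed prices or produce shares. Those points stand. The session discrepancy needs neither assumption.

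**Conclusion.** The contradiction is real. Whether receipt is met, and so which protocol modification follows, can depend on the document used. For trainer sessions this follows from the two rows alone. For food it holds in either direction over the assumed range: the SAP is the easier rule at $10 to $12 per meal without produce, and the harder one at $14 or with substantial produce purchases. How often the verdict would actually differ cannot be judged without prices and ordering data.

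The documents favour the budget measure for food, because a budget is what participants receive. They do not settle whether the session benchmark was meant to stay or whether both must be met. Since no not-feasible verdict hangs on receipt, this should be fixed but does not undermine the trial.

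**What to change.** Reconcile the two rows into one receipt definition, stated identically in both documents.

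1. **Food.** Use the share of available credits spent, with the 80% benchmark. Report meals per week (of 21) and produce bags descriptively.
2. **Trainer sessions.** Restore the 80% benchmark as a separately reported criterion, or state explicitly that it was dropped. The sponsor should confirm whether both criteria must be met.
3. **Unit and denominators.** Say whether 80% is an arm mean, a pooled total or a share of participants. Define eligible sessions, including whether the initial meeting counts and how early delivery is handled.
4. **Transparency.** State when the benchmark changed relative to data review, and show the result under the 21-meal rule as a sensitivity line.

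The cost is a few sentences and one table line. The protocol already plans to record meals, produce bags, exercise sessions and website orders, so no new data are needed. The downside is that, if the session criterion is restored, trainer attendance becomes a benchmark that can be missed.

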### **Usual Care:**

Usual care will consist of the current treatment care that is provided by the participant's prenatal care provider. Usual care consists of a special diet, monitoring of blood glucose levels and encouragement/guidance of increasing a participant's exercise.

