Intervention acceptability	Participants in both conditions will be asked if they would participate again if they	≥80% of participants indicate “likely” or “very likely” on	We will interview participants in the M4M condition who have completed the trial (after delivery) to understand feasibility and acceptability issues and use their feedback to modify study

	had GDM in the future and if they would recommend the program to a friend with GDM (5-item Likert scales of likelihood) 	both measures of acceptability	procedures or intervention materials before moving to a full-scale efficacy trial. We will also examine responses to addition questions assessing frequency of use of and ratings of helpfulness and relevance of other aspects of the M4M intervention.
--	--	--------------------------------	--

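### The 80% intervention-acceptability benchmark is not limited to the M4M arm, so usual-care answers help decide whether it is met

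*SAP*

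**What the plan says.** The Feasibility Outcomes table in the SAP has a row for intervention acceptability. Its measurement cell reads "Participants in both conditions will be asked if they would participate again if they had GDM in the future" and adds whether they would "recommend the program to a friend with GDM". The benchmark is at least 80% "of participants indicate “likely” or “very likely” on both measures of acceptability". The same row in the protocol's Feasibility Outcomes table likewise begins "Participants in both conditions will be asked if they would participate again if they". Neither document names an arm in this benchmark.

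The retention row of the same table does specify the arm: at least 80% "retention in each arm with 65% or less retention indicating that the main trial is not feasible".

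On exposure, the protocol's Usual Care section says "Usual care will consist of the current treatment care that is provided by" the participant's own prenatal provider. The meals, online platform, trainer sessions, activity tracker and scale are all described under the M4M condition.

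Two other passages matter. The opening paragraph of the SAP says "We summarized participant characteristics and feasibility and acceptability outcomes, overall and by treatment condition". The protocol's Post-intervention survey section has both arms rate their experience of the study, and has M4M participants additionally rate the meals and the intervention. No benchmark is attached to those M4M-only ratings.

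**The concern.** A benchmark for whether the intervention is acceptable should rest on people who were offered it. Here half of those randomised were not. A UC participant's willingness to take part again is informative about the trial: randomisation, surveys, dietary recalls. Her willingness to recommend the program is hard to interpret, because the documents do not say what the program means for someone who never received it.

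At stake is whether this one benchmark measures what its title says. UC answers could lift the figure to 80% when M4M participants were lukewarm, or pull it below 80% when they were content. The plan also does not say which of its planned summaries, overall or by condition, is compared with 80%. That leaves the choice open until the results are known.

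**Working it through.** The 80% is a chosen threshold. The documents give no error rate, power or effect size behind it, so there is no derived figure to reproduce. The check is of its consequences.

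**Inputs.** 40 participants randomised 1:1, so 20 per arm (protocol, Sample size and justification; Randomization). Threshold 80% on both items (both Feasibility Outcomes tables). True acceptability by arm is not given and is assumed over 50% to 95% for UC and 70% to 90% for M4M.

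**Pass marks at full response.** Pooled: 0.80 × 40 = 32 of 40. M4M only: 0.80 × 20 = 16 of 20.

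**Counting, pooled reading.**
- M4M 12/20 (60%) and UC 20/20: 32/40 = 80%, met.
- M4M 14/20 (70%) and UC 18/20 (90%): 32/40 = 80%, met.
- M4M 19/20 (95%) and UC 12/20 (60%): 31/40 = 77.5%, missed.
- M4M 20/20 (100%) and UC 11/20 (55%): 31/40 = 77.5%, missed.

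**Counting, each-arm reading.** Each arm needs 16/20. M4M 20/20 with UC 15/20 (75%) is missed. Under this reading UC answers can sink the benchmark but cannot rescue it.

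**Chance of meeting the benchmark, pooled reading.** With a and b the favourable counts in M4M and UC, independent binomials with n = 20 and rates p1 and p2, the chance is the sum of Bin(a; 20, p1) × Bin(b; 20, p2) over all a + b ≥ 32. For M4M alone it is P(a ≥ 16).

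| True M4M rate | UC 50% | UC 60% | UC 70% | UC 80% | UC 90% | UC 95% | M4M alone |
|---|---|---|---|---|---|---|---|
| 70% | 0.005 | 0.03 | 0.11 | 0.30 | 0.59 | 0.75 | 0.24 |
| 80% | 0.02 | 0.11 | 0.30 | 0.59 | 0.87 | 0.95 | 0.63 |
| 90% | 0.09 | 0.29 | 0.59 | 0.87 | 0.985 | 0.998 | 0.96 |

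When both arms are at 80%, the two versions nearly agree (0.59 against 0.63). The disagreement grows as the UC rate moves away from the M4M rate. At M4M 70% and UC 90%, the chance that the pooled figure passes while M4M is below 16/20 is 0.36. At M4M 90% and UC 60%, the chance that the pooled figure fails while M4M is at or above 16/20 is 0.67.

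**With 80% retention (16 respondents per arm).** Pooled: 0.80 × 32 = 25.6, so 26 of 32. M4M only: 0.80 × 16 = 12.8, so 13 of 16. The pooled benchmark is met with M4M 10/16 (62.5%) if UC is 16/16, and missed with M4M 16/16 if UC is 9/16. At a true M4M rate of 70%, the pooled chance runs from 0.008 (UC 50%) to 0.68 (UC 95%), against 0.25 for M4M alone. The pattern is unchanged.

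**The case against.** The strongest reply is that neither document states a pooled rule. They say that both conditions are asked and that 80% of participants should answer favourably; pooling is inferred. This is right as far as it goes. But pooling is the literal reading, and the each-arm alternative still lets UC answers decide the result. Only an M4M-only reading avoids the problem, and nothing in the benchmark points to it.

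A reader might infer that a poor M4M rating would be concealed. The documents do not support that. The SAP commits to summaries by condition, so the M4M percentage will be visible, and M4M participants have their own acceptability items and interviews.

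A reader might also infer that the wrong go/no-go decision on the efficacy trial would follow. That is not supported either. Recruitment and retention have explicit not-feasible cut-offs and this row has none. The follow-on actions in the row draw on M4M interviews and ratings.

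It is fair to say that the larger contrasts above need arm differences of 35 to 40 percentage points, and that no document predicts such gaps. They illustrate the mechanism and are not forecasts. It is also fair to say that asking UC participants whether they would take part again is sensible in a randomised pilot. The follow-up survey is described as enclosed but was not available for review, so its exact wording on the program could not be checked.

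Finally, a reader might infer that dissatisfied drop-outs inflate the figure, since 80% of responders at 80% retention is 0.80 × 0.80 = 64% of those randomised. That is a worst-case bound. It treats every non-responder as unfavourable and assumes every retained participant answered, whereas retention counts completion of any part of follow-up. The documents say nothing about why people would be lost, nor how non-responders enter the acceptability denominator.

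**Conclusion.** The point holds in a limited form. The benchmark labelled as intervention acceptability is not restricted to the arm that receives the intervention, and under either natural reading UC answers help decide whether it is met. At an assumed true M4M rate of 70%, the chance of meeting the pooled benchmark runs from 0.005 to 0.75 as the UC rate goes from 50% to 95%, against 0.24 for M4M alone. These figures assume 20 per arm, full response, independent answers and arm rates that the documents do not supply.

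The impact is moderate. This is a descriptive feasibility pilot, the M4M figure will be reported anyway, and no stop rule depends on this row. The flaw is still more than a missing detail, because the stated criterion can be met or missed on answers from people who never had the program.

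**What to change.** In the intervention-acceptability row of both documents, state that the benchmark of at least 80% favourable on both items is judged in the M4M arm: 16 of 20 at full response, or 13 of 16 at 80% retention. Report the UC answers separately as acceptability of trial participation, with no intervention benchmark. Give the number of M4M non-responders beside the result. Counting them as not acceptable is an optional worst-case bound.

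This needs a few lines of wording and no new data. The price is precision: the benchmark rests on about 20 people instead of 40, so one answer moves it by 5 percentage points instead of 2.5. With 20 respondents it would be met with probability 0.24, 0.63 and 0.96 at true M4M rates of 70%, 80% and 90%, whatever the UC rate.

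The SAP is dated 2/12/2026 and describes the acceptability summaries in the past tense. The documents do not settle whether results had been seen by then. If they had, label the restriction post hoc and report both the pooled and the M4M-only figures.
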